9.6.3.2 Physical examination

Section modified by Amendment 1 (Section 16.1) and Amendment 2 (Modification 14).

A detailed physical examination including height, weight, vital signs (BP, HR), smoking history, alcohol consumption, previous medications, and a pelvic examination will be conducted. Abnormal physical examination findings are recorded either as medical history or as AEs (see Section 9.6.1.1).

9.7 Appropriateness of procedures / measurements

Section modified by Amendment 1 (Section 16.1).

All safety variables and validated PRO instruments, as well as the methods to measure them, are standard variables / methods in clinical studies and / or clinical practice. They are widely used and generally recognized as reliable, accurate and relevant. As described in Table 9–2, subjects completing PRO assessments electronically will receive alerts to complete the scheduled questionnaires prior to the scheduled completion date for each questionnaire. If the questionnaire is not completed by the scheduled date, the subject will receive a second reminder and an alert will be sent to the site. The subject and site will then receive up to 2 additional reminders if the questionnaires are not completed. Subjects completing PRO assessment on paper will not receive alerts.

10. Statistical methods and determination of sample size

10.1 General considerations

All issues concerning subject validity, data consistency checks, permissible data modifications, as well as coding of medical terms and concomitant medication, will be

described in detail in the Data Management Plan. All statistical issues including calculated variables are detailed in the Statistical Analysis Plan (SAP).

The study is observational and does not allow a randomized decision for treatment allocation. Therefore, the allocation of procedure to a subject is driven by preferences, medical decision, medical circumstances, and other information the treating physician requires for the selection of the best option. Allocation bias must therefore be assumed, with consequent potential for confounding. Under such conditions, formal statistical hypotheses of no treatment effect would include an unknown size of bias, as the size of the confounding remains unknown a priori. In particular, the confounding may nullify differences between groups, due to the size of the confounding that cannot be attenuated through analytical methods, but also may inflate differences.

Attempts can be made by analytical procedures to adjust for measured confounding, but still, in this setting, unmeasured confounding cannot be quantified. Several scenarios of analyses are therefore planned to be employed, addressing several of these sources of confounding

It is expected that, due to the recent media attention given to the Essure procedure, there will be significant confounding between the 2 treatment groups leading to channeling bias that will be insurmountable with any analytical method.

The analysis must therefore be considered exploratory in nature.

10.2 Analysis sets

The goal of this study is to assess the various aspects of safety of the procedures studied. Assuming there is adequate overlap in the propensity score (PS) distribution to enable comparisons in the PS confounder-adjusted population between treatment groups, the Adjusted Full Analysis Set will be the primary analysis set.

Safety analysis set

A subject will be included in the safety analysis set if the subject came to the sterilization procedure visit.

Full analysis set

A subject will be included in the Full Analysis Set if she has selected a treatment and, at the time of the procedure, an Essure device has been introduced into the hysteroscope or has an incision / puncture for laparoscopy.

Adjusted Full Analysis Set

Same as the Full Analysis Set, but based on PS confounder-adjusted population. For additional details, see the SAP.

Reliance Set

A subject will be included in the Reliance Set if she has been told to rely on the sterilization method selected at the index event.

Adjusted Reliance Set

Among the PS confounder-adjusted population, a subject will be included if both she and her matched partner are included in the Reliance Set.

10.3 Endpoints and planned statistical analyses

Section modified by Amendment 2 (Modification 3, Modification 25).

The following endpoints will be summarized as part of this study:

- The proportion of subjects reporting AEs of chronic lower abdominal and / or pelvic pain after insertion of Essure System compared to the proportion of subjects reporting AEs of chronic lower abdominal and / or pelvic pain after laparoscopic tubal sterilization. In both groups, AEs due to other apparent etiologies will be identified and excluded.
- The proportion of subjects reporting AEs of AUB after insertion of Essure System compared to the proportion of subjects reporting AEs of AUB after laparoscopic tubal sterilization. In both groups, AEs due to other apparent etiologies will be identified and excluded.
- Proportion of subjects with allergic / hypersensitivity reactions possibly attributed to wearing of Essure devices and allergic / hypersensitivity reactions in women undergoing laparoscopic tubal sterilization.
- Proportion of subjects with newly diagnosed autoimmune disorders in subjects wearing Essure inserts compared to subjects undergoing laparoscopic tubal sterilization.
- Proportion of subjects undergoing invasive gynecologic surgery after Essure placement (excluding second placement attempts), including Essure insert removal compared to the proportion of subjects undergoing gynecologic surgery after laparoscopic tubal sterilization.
- Patient reported outcome measures:
 - MOS SF-36 (Version 2);
 - PROMIS Scale V1.0—Pain Intensity 3a;
 - PROMIS Scale V1.0—Pain Interference 8a Participant Format;
 - AMSS and two intermenstrual bleeding questions used to characterize bleeding in subjects undergoing Essure placement and laparoscopic tubal sterilization;
 - FSQ: to investigate if scores on this instrument (continuous and categorical) correlate with chronic pelvic pain over the course of the study;
 - Supplemental PRO Questionnaires – a series of PRO tools used to actively solicit information on AEs commonly found in MDR reports with Essure;
 - Social Media Questionnaire – to elicit information about sources of influence on medical decisions, in particular, use of social media.

- Rates of AEs in subjects undergoing Essure placement and laparoscopic tubal sterilization;
- Characteristics of physicians performing the procedures;
- Characteristics of subjects undergoing Essure Confirmation Test compared to subjects who do not comply with the requirement for Essure confirmation testing.

Statistical analyses will be explorative and descriptive in nature and no confirmatory hypothesis tests are intended to be performed; p-values will be interpreted as a metric for uncertainty. Therefore, no adjustment for multiplicity will be necessary.

All endpoints and variables will be analyzed by descriptive statistical methods. The number of data available and missing data, mean, standard deviation, minimum, lower and upper quartiles, median, and maximum will be calculated for continuous data. Frequency tables will be generated for categorical data. They will include the number of missing values as additional categories. Relative frequencies will be shown as percentages which will be calculated as a proportion including the category of missing values. Incidence rates and proportions will be used to summarize main endpoints and other variables. For time-to-event endpoints, hazard ratios derived from a Cox regression model, and Kaplan-Meier estimates will be provided.

If not specified otherwise, the analyses are presented in a way that events will be assigned to the treatment which was given initially at the index event.

The main analyses will be performed on a PS confounder-adjusted population of the Full Analysis Set in order to adjust for measured confounding as well as on the Full Analysis Set population. After all subjects have been enrolled, an outcome-blinded independent party, which only has access to the treatment variable and baseline variables, will perform the PS matching. All baseline variables will be considered for inclusion into the model; however, the following variables have shown previous evidence to likely be included in the model: age, race, BMI, US geographical region, insurance, hormonal contraception use at baseline, pre-existing pain disorders (pelvic pain, low back pain, chronic headache, fibromyalgia), disorders associated with hysterectomy (fibroids, ovarian pathology, endometriosis, prolapse, hyperplasia), gastrointestinal disorders (e.g., irritable bowel syndrome), pre-existing autoimmune disease, pre-existing diabetes, and pre-existing hypertension.

For subjects with a second placement procedure, any PROMIS 3a and 8a PRO data collected after baseline and up to and including Month 3 will be repeated based on the timing of the second placement procedure (See Section 9.2.2.3 for additional details). For summaries by time point (e.g., Week 1), only the final evaluation will be included in the analyses. For time-to-event endpoints or proportion of subjects meeting a given criterion, all collected data will be used.

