5.2 Endpoints and variables

5.2.1 Main endpoints

Section modified by Amendment 1 (Section [16.1](#)) and Amendment 2 ([Modification 3](#), [Modification 4](#), [Modification 5](#), [Modification 7](#)).

- **Pain:** The proportion of subjects reporting AEs of chronic lower abdominal and / or pelvic pain after insertion of Essure System compared to the proportion of subjects reporting AEs of chronic lower abdominal and / or pelvic pain after laparoscopic tubal sterilization. Total incidence of pain events will be based on AE reporting. If a potential pain event is spontaneously reported outside of a scheduled visit or scheduled patient-reported outcome (PRO) tool administration, the pain PRO tools (Patient-Reported Outcomes Measurement Information System [PROMIS] Scale V1.0 – Pain Intensity 3a and PROMIS Scale V1.0 – Pain Interference 8a Participant Format; see Section [9.2.3](#)) will be administered off-schedule in order to characterize pain intensity and interference. If during the course of a scheduled PRO administration (see [Table 9–2](#) and Section [9.2.3](#)) the subject reaches a preset threshold for pain on a PRO tool, even if she has not spontaneously reported a pain event to the investigator, the investigator will be alerted and instructed to investigate this finding in order to determine whether or not an AE has occurred. Standard criteria for AE assessment (e.g., new or worsening symptom) will be used and all investigators will be trained on standard AE assessment.

The preset thresholds that will trigger investigation of pain as an AE are as follows: on the PROMIS Pain Intensity Scale, a score of 3 (moderate intensity) for the ‘pain at its worst’ question will trigger investigation regardless of the other scores or results of the PROMIS Pain Interference Scale. For PROMIS Pain Interference Scale, a t-score of ≥ 60 (which corresponds to a raw score of ≥ 22) or any single item raw score of ≥ 4 will trigger investigation regardless of the results of the PROMIS Pain Intensity Scale. Section [9.2.3](#) includes justification for these thresholds. Not all reports of pain that are reported on the PRO tool will be considered AEs. This is particularly notable in the case of a subject who has pre-existing pain that continues to be unchanged post-sterilization procedure.

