- In addition, any subject who experiences an AE of pelvic / lower abdominal pain in this study will be evaluated for possible hypersensitivity / allergic reaction including central laboratory evaluation and case adjudication (see below for further details on hypersensitivity / allergy).

Per the definition by the American College of Obstetricians and Gynecologists, chronic pelvic pain is pain in the pelvic area that lasts for 6 months or longer. In those subjects reporting lower abdominal / pelvic pain at any time during the study, either spontaneously or in response to the regularly scheduled PRO tool and who have been judged to have experienced an AE, it will be determined if duration of the pain meets this definition. The percentage of subjects in each group (laparoscopic and hysteroscopic) who are determined to have new onset or worsening chronic pelvic / lower abdominal pain will be reported. Additional analyses will be carried out looking at total number of pain reports (regardless of chronicity), intensity, and pain interference.

- **Bleeding:** The proportion of subjects reporting AEs of abnormal uterine bleeding (AUB) after insertion of Essure System compared to the proportion of subjects reporting AEs of AUB after laparoscopic tubal sterilization. Total incidence of new onset or worsening abnormal bleeding events will be based on AE reporting. If a potential bleeding AE is reported at a scheduled visit or if the subject spontaneously reports such an event to the site at some other time, the event will be evaluated per standard AE assessment. In the event of a report outside of a scheduled visit or scheduled PRO administration, the Aberdeen Menorrhagia Severity Scale (AMSS) and two intermenstrual bleeding questions will not be re-administered as the recall period for these PRO tools is 3 months and these data are captured during the scheduled PRO tool administration which occurs every 3 months.

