10.5 Planned interim analyses - amended

Section added by Amendment 2 (Modification 26) and Amendment 3 (Modification 1).

Section modified by Amendment 4 (Modification 2 and Modification 4)

Three interim analyses will be performed. The first will be initiated at the end of enrollment, the second will be initiated after all subjects complete 1 year of follow-up, and the third will be initiated at the point all subjects complete 3 years of follow-up. The purpose of these analyses is to formally review study data, at the request of FDA.

The following will be summarized as part of these interim analyses:

- Demographic information listed in Section 9.3.1.
- The proportion of subjects reporting AEs of chronic lower abdominal and / or pelvic pain after insertion of Essure System compared to the proportion of subjects reporting AEs of chronic lower abdominal and / or pelvic pain after laparoscopic tubal sterilization.
- The proportion of subjects reporting AEs of AUB after insertion of Essure System compared to the proportion of subjects reporting AEs of AUB after laparoscopic tubal sterilization.
- Proportion of subjects with allergic / hypersensitivity reactions possibly attributed to wearing of Essure devices and allergic / hypersensitivity reactions in women undergoing laparoscopic tubal sterilization.
- Proportion of subjects with newly diagnosed autoimmune disorders in subjects wearing Essure inserts compared to subjects undergoing laparoscopic tubal sterilization.
- Proportion of subjects undergoing invasive gynecologic surgery after Essure placement (excluding second placement attempts), including Essure insert removal compared to the proportion of subjects undergoing gynecologic surgery after laparoscopic tubal sterilization.
- Rates of AEs in subjects undergoing Essure placement and laparoscopic tubal sterilization.
- Device removals, and outcomes and resolutions, when associated with an AE.

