**Table 2 - Outcome endpoints and variables collected during treatment**

	Endpoint/Variable
Main Endpoints	
 
Subjects reporting AEs of chronic lower abdominal and/or pelvic pain after sterilization procedure
 
Subjects reporting AEs of abnormal uterine bleeding after sterilization procedure
 
Subjects with reported allergic/hypersensitive reactions
 
Subjects with newly diagnosed autoimmune disorders
 

	Endpoint/Variable
	
 
Subjects undergoing invasive gynecologic surgery (e.g., device removal or hysterectomy) after sterilization procedure (excluding second Essure placement attempts)
 

Patient Reported Outcomes	
 
MOS SF-36 (Version 2) which includes eight distinct health domains (physical function, role-physical, bodily pain, mental health, role-emotional, social functioning, vitality, and general health perceptions) and physical component summary and mental component summary scores
 
PROMIS Scale V1.0—Pain Intensity 3a, raw score, T-Scores, percentages of subjects who had T-Scores more than 50 and 60
 
PROMIS Scale V1.0—Pain Interference 8a, raw score, T-Scores, percentages of subjects who had T-Scores more than 50 and 60
 
AMSS and two intermenstrual bleeding questions used to characterize bleeding in subjects undergoing Essure placement and laparoscopic tubal sterilization, total raw scores and individual score for each question, percentage of subject having total scores greater than 40
 
FSQ: to investigate if scores on this instrument (continuous and categorical) correlate with chronic pelvic pain over the course of the study
 
Supplemental PRO Questionnaires
 
Social Media Questionnaire
 

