Adverse Events	Any AE, Serious AEs, reason for serious AE, AE of special safety interest, AE intensity, AE related to study procedures or devices, type of procedure/device related to AE, AE outcome, pre-existing condition, concomitant medication, other non-study procedures
Contraceptive Method Post-procedure	Method used for contraception, duration of the contraceptive method used.
Concomitant Medication	Type of medication, main indication for medication
Additional Abdominal or Pelvic Surgery	Type of surgery performed, was surgery done for the purpose of sterilization/ re-sterilization , surgery due to an AE
Allergy/Hypersensitivity Evaluation, Autoimmune Disorder Evaluation, and PRO Alert Response	Symptom subjects reported, adjudication committee form, pathological findings, serum or plasma nickel and titanium levels, NiLPT and chromium LPT results, cytokine samples analysis , type of alert, pain alert response and bleeding response.
Study Completion	Did subject complete study, primary reason for premature discontinuation, time to premature discontinuation
Death	Number subjects died

a Only measured for Essure Group

b Only measured for laparoscopic tubal sterilization group

For the main outcomes, [Table 3](#) lists the SMQ search terms for abnormal uterine bleeding and lower abdominal and/or pelvic pain. Per the definition by the American College of Obstetricians and Gynecologists, chronic pelvic pain is pain in the pelvic area that lasts for 6 months or longer (i.e., the stop date of the pain minus start date is longer than 182 days, or by the time of EOS, the subject still has pain ongoing with start date 182 days before EOS).

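### Protocol 10.3 excludes chronic pain and bleeding AEs attributed to another cause, but the rest of the protocol and the SAP define the same main endpoints without that rule, and nothing says how it would be applied

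*Protocol*

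**What the plan says.** The exclusion appears once in the current endpoint text, in protocol 10.3, attached in identical words to the chronic pain and the AUB endpoints: "In both groups, AEs due to other apparent etiologies will be identified and excluded".

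The other definitions do not carry it:

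- **Protocol synopsis (main variables) and 5.2.1.** Both rest on AE reporting. For pain: "Total incidence of pain events will be based on AE reporting". For bleeding: "Total incidence of new onset or worsening abnormal bleeding events will be based on AE reporting".
- **Protocol 10.5 (interim analyses).** The same proportions are listed without the exclusion, for example "The proportion of subjects reporting AEs of AUB after insertion of Essure System compared to the proportion of subjects reporting AEs of AUB". SAP section 7 does likewise.
- **SAP Table 2.** The main endpoints are "Subjects reporting AEs of chronic lower abdominal and/or pelvic pain after sterilization procedure" and "Subjects reporting AEs of abnormal uterine bleeding after sterilization procedure".
- **SAP 6.4, text after Table 2.** Events are found by coded term: Table 3 "lists the SMQ search terms for abnormal uterine bleeding and lower abdominal and/or pelvic pain". Pain must also be chronic, meaning that "the stop date of the pain minus start date is longer than 182 days", or that it is still ongoing at end of study with a start 182 days before.

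SAP 6.2 drops AEs that adjudication does not validate, but does not say which endpoints this concerns.

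**The concern.** A team that follows protocol 10.3 removes some events from the numerator; a team that follows the SAP keeps them. Both could report the result as the main pain or bleeding endpoint. These are two of the five main endpoints in SAP Table 2, and SAP 6.4 reserves comparative analysis for main endpoints.

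The affected share need not be small. Table 3 includes lower back pain, dysmenorrhoea, dyspareunia and amenorrhoea, and exclusion criterion 10 lets women with existing pelvic pain or menorrhagia enrol at the investigator's discretion. Many events could have an arguable other cause.

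If the exclusion is applied, unequal application between groups biases the comparison. Protocol 5.2.1 itself expects that outside influences such as social media may make AE reporting differ by group. The chance of finding another cause may differ too (my inference): SAP Table 2 records intraoperative findings for the laparoscopic group only, and ultrasound or hysterosalpingogram findings for the Essure group only.

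Interim summaries by group, defined without the exclusion, come before the final report. An unsettled definition therefore leaves room to choose after results have been seen.

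**Working it through.** **1. Is this current text?** Yes. The sentence stands in protocol 10.3, not only in an amendment log. Section 10.3 is marked as last modified by Amendment 2. SAP 1.2 lists amendments up to Amendment 3, so the sentence's section was already in its current form for the SAP authors.

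**2. Does anything else implement the rule?**

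| Candidate | What it does | Implements 10.3? |
|---|---|---|
| Protocol 5.2.1, new-or-worsening criterion | Keeps unchanged pre-existing symptoms from becoming AEs | No; it concerns change, not cause |
| SAP 6.1.3 and 6.4 | Limit events by treatment emergence and risk period | No |
| SAP Table 3 and the 182-day rule | Select by coded term and, for pain, duration | No stated rule on cause |
| SAP 6.2 | Drops non-validated AEs, endpoints not named | Not established; see step 3 |
| SAP 6.5.1 (adverse events) | Extra tables, including procedure-related pain and bleeding | No; these are not the main endpoints |
| SAP 6.8 | Lifts censoring | No |

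**3. Could the adjudication committee do it?** Protocol 14.3 and SAP 6.4 give it allergy/hypersensitivity and autoimmune events. It reviews pelvic pain only for a possible hypersensitivity element, and AUB is not in its remit. The nearest comparable judgement is the investigator's causality assessment in protocol 9.6.1.2.6, where a negative answer covers a highly likely competing cause. Neither 10.3 nor the SAP links that assessment to the main endpoints.

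**4. Size.** The documents give no event rate, sample size or power for these endpoints, so there is no figure to reproduce. All inputs below are assumptions. Each affected woman is treated as having one qualifying event. With eE and eL the shares of events excluded in the Essure and laparoscopic groups:

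RR after exclusion = all-cause RR × (1 − eE) / (1 − eL)

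At an equal all-cause risk of 15% (true RR 1.00):

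| eE / eL | Essure | Laparoscopic | RR | Risk difference |
|---|---|---|---|---|
| 30% / 30% | 0.15 × 0.70 = 10.5% | 10.5% | 1.00 | 0 |
| 40% / 50% | 0.15 × 0.60 = 9.0% | 0.15 × 0.50 = 7.5% | 1.20 | +1.5 points |
| 30% / 50% | 10.5% | 7.5% | 1.40 | +3.0 points |
| 20% / 50% | 0.15 × 0.80 = 12.0% | 7.5% | 1.60 | +4.5 points |
| 50% / 30% | 7.5% | 10.5% | 0.71 | −3.0 points |
| 40% / 20% | 9.0% | 12.0% | 0.75 | −3.0 points |

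The RR does not depend on the 15%; the risk difference scales with it.

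**5. Unbiased exclusion also changes the ratio.** Assume sterilization-attributable risks of 4% (Essure) and 2% (laparoscopic), plus the same background b from other causes in each group. After perfect exclusion RR = 4/2 = 2.00. All-cause, b = 2% gives 6/4 = 1.50 and b = 10% gives 14/12 = 1.17. The risk difference is 2 points under both definitions.

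**The case against.** **Silence is not a contrary definition.** Protocol 5.2.1 names AE reporting as the data source; it has no search list and does not say that cause is ignored. One can read 10.3 as a rule that was never implemented rather than as a rival endpoint. That is fair as to wording, but the numerators still differ according to which text is followed.

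**The SAP does not count everything.** It needs a Table 3 term, treatment emergence, the risk period and, for pain, the duration rule. Table 3 is almost entirely symptoms, so an AE coded only to a diagnosis such as endometriosis would not count. The list may thus achieve part of the exclusion. The SAP does not say so, however, and a symptom coded separately would still count.

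**A stronger reading is that the exclusion would be judged with the group known.** A reader might infer this from the open-label design and from protocol 7.3, where blinding does not apply. The documents do not say it, because they name no judge and no process. What they support is that judge, criteria, timing and masking are all unspecified.

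**The all-cause endpoint is not masked either.** Under 5.2.1 the investigator decides whether an AE has occurred at all. That stands: the proposed change removes one layer of unmasked judgement, not all of it.

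**The study is exploratory and much is tabulated anyway.** SAP 6.5.1 shows all treatment-emergent pain and bleeding AEs and the procedure-related subsets, and every AE is listed. This lowers the severity. It does not settle the main endpoint: the pain tables are not limited to chronic pain, and none applies the 10.3 rule.

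**Conclusion.** The inconsistency is real and should be resolved before the final analysis. It does not invalidate the study. Protocol 10.3 calls for an exclusion by cause that no other endpoint text contains, that the SAP does not implement, and that has no operating rule.

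The size cannot be taken from the documents. Under the assumed shares above, unequal exclusion turns no difference into risk ratios from 0.71 to 1.60, and equal exclusion leaves 1.00. Nothing in the documents indicates which direction is more likely. Even error-free exclusion would change the proportions and the ratio, because the two definitions measure different things.

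No confirmatory test is planned, so the consequence is possible bias, doubt about what the main result means, and room to choose between definitions. It does not bear on type I error or power.

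**What to change.** 1. In SAP 6.4, state that the main pain and AUB endpoints count every treatment-emergent Table 3 AE in the risk period, with the existing duration rule for pain, whatever cause is attributed to it. Align protocol 10.3 with this and with the synopsis, 5.2.1 and 10.5.
2. Keep the idea behind 10.3 as a named sensitivity analysis in SAP 6.8. Use a list of MedDRA diagnoses fixed before the final analysis and applied without reference to group. Report the excluded events by group and reason.
3. Limit the exclusion in SAP 6.2 to the allergy/hypersensitivity and autoimmune endpoints.

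The documents do not themselves settle which definition should lead. The all-cause count is proposed because it is what the SAP already specifies and it needs no further judgement of cause.

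The cost is wording in both documents, one term list and one extra table. There are two downsides. The all-cause endpoint is less specific to the sterilization. The diagnosis list still depends on diagnoses entered by unmasked investigators, so in the sensitivity analysis it reduces the bias rather than removing it.
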